**Document date: 6.16.2023** 

#### SPECIFIC AIMS

Hypnotics such as benzodiazepines and benzodiazepine receptor agonists (BzRAs or Z-drugs) are often prescribed for insomnia. Among Veterans attending outpatient clinic appointments, approximately one-quarter use hypnotics (or bedtime alcohol). Hypnotics use is associated with an increased risk of falls and worse cognition in older adults. Discontinuing hypnotics often attenuates or reverses these negative effects, and the Department of Veterans Affairs (VA) has initiatives to reduce hypnotic use among older Veterans. Current discontinuation strategies focus on tapering off the hypnotic and/or treating insomnia symptoms. Common strategies include supervised gradual taper (SGT), cognitive behavioral therapy targeting hypnotic withdrawal (CBT-HW), cognitive behavioral therapy for insomnia (CBTI), and combination therapy (SGT+CBTI). Yet up to 40% of patients eventually resume use of hypnotics with these strategies, suggesting that other mechanisms need to be targeted to achieve and sustain high rates of non-use.

Another mechanism that may be a viable target for achieving hypnotic discontinuation and sustaining long-term non-use is the placebo effect,  which is characterized by real improvements in sleep arising from psychosocial aspects of treatment rather than drug effects alone. We recently developed and tested the feasibility of an intervention that targets the placebo effect. Our intervention retains core components tested in prior studies for achieving hypnotic discontinuation (i.e., SGT+CBTI), but adds a novel feature—"masked" tapering. Masking is achieved by encapsulating hypnotics (prepared by a compounding pharmacy) so the patient, who has consented to a gradual taper, is unaware of the actual dose in each capsule until the end of the taper, when the tapering schedule is revealed to the patient. Towards the end of the taper, placebo capsules are used. Through novel cognitive exercises, the therapist uses masking as a tool to challenge expectancies about hypnotics, which may be contributing to chronic use, and to augment CBT-HW (e.g., preparing for withdrawal). Coupled with CBTI (i.e., stimulus control, sleep restriction, cognitive therapy for insomnia, and relaxation), the intervention targets the placebo effect and the factors contributing to insomnia symptoms and helps patients safely taper off their hypnotic and develop relapse prevention skills.

The objective of the proposed study is to test whether hypnotic discontinuation rates can be increased with a novel set of cognitive exercises that use supervised masked tapering as a core tool to challenge expectancies about hypnotics. In a 4-year randomized trial (N=132 participants), we will measure the effects of a 2-month program entitled, **M**asked **T**aper plus **c**ognitive behavioral therapy-**a**ugmented **p**rogram (MTcap), which combines novel cognitive behavioral therapy exercises, supervised masked hypnotic tapering, CBT-HW, and CBTI. We will compare outcomes in MTcap to a supervised unmasked (traditional) SGT+CBTI program post-treatment and at 6 months follow-up to determine whether the addition of the novel cognitive exercises and masked tapering reduces expectancies for hypnotics, improves hypnotic discontinuation rates, and improves insomnia symptoms. The rationale is that hypnotic-related placebo effects can be specifically targeted with our novel intervention. The following are the **primary aims** for the proposed project:

Aim 1: Determine whether MTcap improves hypnotic discontinuation more than SGT+CBTI post-treatment and at 6 months follow-up.

- H1a: Participants who receive MTcap will have increased likelihood of hypnotic discontinuation posttreatment and at 6 months follow-up compared with those who receive SGT+CBTI.
- H1b: Participants who receive MTcap will use less hypnotic medication post-treatment and at 6 months follow-up compared with those who receive SGT+CBTI.
- Aim 2: Determine whether MTcap improves insomnia severity more than SGT+CBTI at 6 months follow-up.
- H2: Participants who receive MTcap will have lower Insomnia Severity Index scores at 6 months follow-up compared to SGT+CBTI.
- Aim 3: Determine whether MTcap improves expectancies about hypnotics more than SGT+CBTI post-treatment and at 6 months follow-up.
- H3: Dysfunctional Beliefs and Attitudes About Sleep (DBAS) Medication Scale ratings will improve compared to SGT+CBTI post-treatment and at 6 months follow-up.

A secondary aim is to compare balance and cognition in the MTcap arm compared with the SGT+CBTI arm at follow-up. We hypothesize that participants who receive MTcap will have better balance and cognition compared to those who receive SGT+CBTI post-treatment and at 6 months follow-up.

This proposed study will test the effects of an innovative intervention on chronic hypnotic use among older Veterans, which is a prevalent, high-priority, and challenging problem. The intervention was designed based on extensive feasibility testing. If successful, this novel intervention could lead be disseminated throughout the VA and lead to significant improvement in ongoing efforts to decrease chronic hypnotic use among older Veterans.

#### **RESEARCH DESIGN AND METHODS**

Basic Study Design (Figure 1): The proposed study is a 4-year randomized trial to test the efficacy of a novel treatment program for achieving hypnotic discontinuation among older Veterans receiving outpatient prescriptions for hypnotics.

Setting: The proposed study will be performed within the VAGLA, where approximately 1,650 older Veterans receive each quarter the benzodiazepines and Z-drugs targeted in this study. All in-person study assessments and treatment sessions will be completed within VAGLA.

Specific VAGLA facilities include: West Los Angeles Medical Center, Sepulveda Ambulatory Care Center, Los Angeles Ambulatory Care Center and VA Community-based Outpatient Clinics in Lancaster, Oxnard, and Bakersfield. Our research staff may meet participants to drop/off or pick up study materials, and if necessary, to conduct baseline and follow-up assessments. Recruitment sample:

The sampling frame for this study will consist of Veterans ≥ 55 who received hypnotic prescriptions for three or more months from VAGLA pharmacies within the past year. To obtain this sample we will access VA administrative data sources, seek patient referrals from VAGLA healthcare providers, and distribute recruitment flyers in VA GLAHS outpatient clinics. Each of these recruitment strategies is described below:

[figure not shown]
1. VA Corporate Data Warehouse (CDW) Authorized VA project team member(s) will work with VINCI programmers to pull a sample using the VA Corporate Data Warehouse

(CDW). Study inclusionary criteria will be applied to select eligible Veterans for recruitment. To help capture eligible patients with fresh contact information, this process will be repeated at least 2-3 time during the study recruitment period.

The variables in the sample file will include the following:

- Unique patient identifiers (e.g. Scrambled SSN, Patient ICN, PatientSID, etc.)
- Contact information (e.g. Name, residential address, zip code, telephone numbers)
- Demographic and Veteran Characteristics information (e.g. date of birth, gender, race/ethnicity, date of death, Veteran status)
- Hypnotic medications (e.g. outpatient medication names, dose, prescription number, issue date, etc.) A link file will be created using the sample file to associate the project specific study ID with the Veterans' unique identifier (PatientICN/PatientSID, or SSN/scrambled SSN) which can be used to access VA VINCI/CDW data. The new records pulled with each additional sample pull will be added to our link file to create a single cumulative file of all sampled Veterans. All records will be assigned a study ID number that will serve as the primary key for matching data from the additional sources. The Link File will be stored on a restricted-access folder on the CSHIIP-managed secure server behind the VA firewall and is never transferred during the project, nor will it be accessible to anyone other than authorized VA project team member(s).

We will use the same process to identify from CDW Veterans who receive care at the Tibor Rubin VA Medical Center in Long Beach (VALB). Many VALB patients live close to the VAGLA campus in West Los Angeles and may be willing to participate in the study. If these VALB Veterans enroll in the study, all study activities will be conducted at VAGLA. No study activities will be done at VALB.

We will also use the same process to identify from CDW Veterans who receive care at the VA Loma Linda Healthcare System. If these Loma Linda Veterans enroll in the study, study activities will be conducted via telehealth at VAGLA.

2. VA Academic Detailing Service Benzodiazepine/ZDrugs Dashboard

The VA Academic Detailing Service has compiled and maintains a database of VA GLAHS patients who are prescribed benzodiapezines and benzodiapezine receptor agonists (Z-drugs). This database, or dashboard, can be found on their Data Resources website. In this dashboard, the names and mailing addresses of VA GLAHS patients prescribed benzodiazepines and Z-drugs are listed along with prescribing information. We will access this dashboard to confirm the CDW sample.

The variables that will be abstracted from the dashboard will include:

- Unique patient identifiers (PatientSID, last 4 SSN)
- Contact information (name, residential address, zip code)
- Patient characteristics (age)
- Hypnotic medications (medication names, number of prescriptions, prescriber, dispensing location, prescribed for insomnia or PTSD, next primary care and mental health appointment dates and locations)

# 3. Consults to VAGLA Insomnia clinics

Research staff will access the VA electronic consults made to Insomnia clinic. Patients who are referred to the clinic for cognitive behavioral therapy for insomnia treatment will be identified. Study staff will then review demographic information, medications and clinic notes to determine basic eligibility criteria (e.g., age ≥ 55, prescribed a hypnotic medication) of these Veterans. Names, addresses and telephone numbers of Veterans who meet these basic eligibility criteria will be abstracted from the medical record by research staff and entered into a study database.

# 4. Referrals from VA GLAHS healthcare providers

A recruitment flyer with a cover memo to VA GLAHS providers with be distributed to providers in primary care, mental health, and sleep medicine clinics (see attached Provider Memo and Recruitment Flyer). The memo describes the study and basic eligibility criteria and invites providers to distribute the flyer to patients who might be appropriate for the study. Providers are also invited to send an encrypted email to the study team with the name and last four social security numbers of patients who may be eligible for the study. When the research team receives the name of a patient from a provider, research staff will review the CPRS electronic medical record to determine if the patient meets the basic study eligibility criteria (e.g., age, prescribed one of the targeted hypnotics to treat insomnia) (see CPRS data abstraction form). Patients who meet these criteria will receive a recruitment telephone call from research staff as described below (see telephone eligibility screening).

# 5. Self-referral from Veterans

We will also post the recruitment flyer (which may also be enlarged to the size of a poster board) in outpatient clinic waiting areas (our research team will seek approval from appropriate VA GLAHS authorities prior to displaying any flyers/posters) and at community sites frequented by Veterans (e.g., Veteran Centers, DAV halls, Elk Lodges, senior centers). Written permission to post the recruitment flyer at community sites, and for study staff to provide verbal information about the study, will be obtained from each site (see attached Off-site Permission form) before flyers are posted.

6. e-Recruitment: We will put information about the study on VA Greater Los Angeles Facebook, VA Greater Los Angeles Twitter, and the new VA Greater Los Angeles Research and Development website (see attached social media announcements). Patients who are interested in the study will be advised to call the study office to learn more about the study.

If a Veteran calls the study office in response to seeing a flyer, poster, social media announcement, or receiving a flyer from a provider, research staff will follow the protocol described below (see telephone eligibility screening).

Table 1. Inclusion and Exclusion Criteria

Inclusion criteria:

# Inclusion and Exclusion Criteria

Table 1 lists the inclusion criteria for the sampling frame and enrollment into the study. We anticipate enrolling up to 600 participants and randomizing 132 to receive the intervention. Exclusion criteria for enrollment and randomization are also listed in Table 1.

# Recruitment, enrollment

#### Recruitment letter

Veterans identified from the CDW database will be mailed a recruitment letter and opt-out card (see Recruitment letter and Opt-out card). Veterans will be asked to return the opt-out card in a postage-paid envelope within 7 days of the letter mail date to indicate whether they wish to be called by our research staff. The letter will explain that research staff will call the Veteran if the opt-out card is not returned within the 7day timeframe. In total, we plan to send this recruitment package to approximately 2500 older Veterans over the first three years of the study.

We will obtain a revised list from both databases throughout the first 3 years of the study as new names are needed for recruitment. This process will enable us to have a current list of names for our sample. In our previous work, we found that Veterans with a visit in the prior 2 quarters were more likely to have a valid mailing address and to participate in research than Veterans who had not received care in that timeframe.

Study staff will telephone potential participants who

## Telephone eligibility screening

were sent the recruitment letter but did not return the "opt out" card. They will also telephone Veterans who were referred to the study by a VA provider. Staff will leave up to 4 telephone messages. Veterans who do not return our call after the 4 messages will be considered as "not interested" in participating. During this telephone call, the study will be explained and verbal consent for screening will be obtained from Veterans who express interest in the study (see Telephone Screening Script). Additional eligibility criteria will be assessed with a structured screening questionnaire (see Telephone Screening Questionnaire). The screening questionnaire will include items to assess the following: 1) current insomnia symptoms, 2) hypnotic use, 3) number of months and nights per week hypnotic is used, 3) major health events (e.g., surgery) within the past month (individuals with a recent major event will be re-contacted 3 months later), 4) housing situation (e.g. homelessness), 5) access to transportation to the medical center, 6) perceived physical, emotional or substance use being a barrier to participating in the study sessions. The same script and telephone screening questionnaire will be used for Veterans who call the study office in response to the recruitment flyer. Following completion of the telephone screening questionnaire, eligible and interested Veterans will be scheduled for an initial meeting (in-person or by video) to obtain written informed consent. Potential participants also will be informed that they can receive a blank written informed consent form in the mail to provide them with sufficient time to consider participation and discuss participation with family members, should they so desire.

During the telephone screening, potential participants will also be informed that prior to the consent visit, research staff will review their CPRS medical record to identify hard exclusion criteria, such as clear diagnosis of bipolar disorder, substance abuse, benzodiazepine/z-drug doses that are supratherapeutic, or untreated severe obstructive sleep apnea. Participants who have any of these exclusionary criteria will be informed that they currently do not meet study inclusion/exclusion criteria and the in-person or VVC consent appointment will be cancelled.

- Age > 55 years
- · Use of lorazepam, alprazolam, temazepam, clonazepam, and/or zolpidem for current or prior insomnia symptoms 2 or more nights per week for at least
- · Current or prior insomnia symptoms
- Available to attend weekly in-person or video sessions over 9 weeks

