#### Exclusion criteria:

ligh risk for complications in outpatient hypnotic discontinuation program:

- · Seizure disorder
- Supratherapeutic/high baseline hypnotic dose (> diazepam-equivalent of 8 mg/night). Note that for individuals on > 1 of the targeted hypnotics, total baseline dose in diazepam-equivalents will be calculated & if > 8 mg/night, individual will be excluded.
- · High risk of complicated withdrawal; benzodiazepine intoxication or current or past symptoms of complicated benzodiazepine/alcohol withdrawal (e.g., seizure, delirium at baseline)
- · Polydrug use (e.g., chronic high dose opioids)
- Unable to keep study medications in secure location
- · Evidence of prescription fraud (e.g., multiple prescriptions for same drug filled at VA and non-VA pharmacies, diversion)

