#### Randomization

Individuals who complete the baseline assessment and meet all inclusion/exclusion criteria will be randomly assigned to one of the two intervention groups: MTcap (N=66) or SGT+CBTI (N=66). Both interventions are described below. Randomization procedures will follow the CONSORT criteria for randomized trials. Stratified

randomization will be used to ensure that both groups are balanced in baseline hypnotic drug type half-life (i.e., temazepam/zolpidem; alprazolam/lorazepam; clonazepam) and gender. The study statistician will generate the stratified randomization sequence. A set of envelopes containing the group assignment will be generated and stored in a secure file drawer accessible only authorized staff. Once final eligibility is determined, the data manager will open the next envelope in sequence within the appropriate stratum.

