# Extended taper plan

We have identified specific situations when the taper plan may need to be modified:

- a. Withdrawal symptoms/extended taper required: The taper may be extended up to a maximum of 16 weeks if the participant has withdrawal symptoms or cannot tolerate the scheduled taper, based upon changes in several of the CIWA-B items and vital signs, along with the patient's, interventionist's, and study physicians' judgments. In the MTcap group, an extended taper may be achieved by giving a duplicate 7-day blister pack (e.g., plateauing the doses until the participant is ready to move to the next blister pack). In the SGT+CBTI group, participants will be instructed to repeat a particular week in the printed taper schedule. Participants will continue to be monitored with weekly CIWA-B, vital signs, and the interventionist will review and reinforce key content of the intervention.
- b. Hypnotic dosed as "prn" at baseline: Taper schedules for participants who used their hypnotic "as needed" at baseline will be adjusted so that the starting week's total weekly hypnotic dose does not exceed the participants' total weekly baseline hypnotic dose.

For the MTcap group, the capsules on the predetermined drug-free days will be filled with an inert filler substance. The participants will still be instructed to take the capsule on a scheduled based nightly, not as needed. The use of capsules will ensure that the participant is not exposed to the drug more frequently than the baseline exposure. An increase in adherence to the taper protocol is one rationale for using capsules filled with inert filler substance rather than instructing participants not to take any capsule at all (i.e., similar to oral contraceptive inert pills that are provided in the monthly oral contraceptive pill pack). Another rationale for using insert capsules is related to our study's objective, which aims to develop an intervention for reducing placebo effects, such as the effects related to the conditioned response of taking the drug and attributing sleep and daytime function—which are known to vary from day to day—to the act of taking the pill.

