# Primary Analysis Plan

We plan to randomize 132 individuals, of whom we expect 13% to drop out (i.e., fail to complete assessments) by 6-months, yielding N=114 participants with complete data ( $\sim$  57 per group). We base this drop-out on our completed study ([name] VA Merit 08-295). We will include terms for stratification characteristics and covariates for baseline pain intensity, PHQ-9, and opioid use in all of the models. All analyses below assume  $\alpha$ =0.05, power=0.80, two-sided hypothesis tests, and intention-to-treat approach. Effect sizes are in the measure's natural units and Cohen's d (large=.8; medium=.5; small=.2).

- (H1a) Participants who receive MTcap will have increased likelihood of hypnotic discontinuation post-treatment and at 6 months follow-up compared with those who receive SGT+CBTI: Hypnotic discontinuation (yes=1/no=0) will be regressed on treatment group assignment (MTcap vs. SGT+CBTI) in two logistic regression models (post-treatment and 6 months follow-up). Sample size calculations establish that 114 participants will be adequate to detect a difference of 21% to 26% between the MTcap and SGT+CBTI groups, depending upon the discontinuation percentage of the SGT+CBTI group (59% to 63% at follow-up in prior studies). In our feasibility study, 100% discontinued hypnotics post-treatment. We will use multiple imputation.

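### The H1a discontinuation models omit baseline hypnotic use, which the trial already collects and uses in H1b; this loses some precision but does not bias the result

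*Combined protocol and SAP*

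**What the plan says.** **Who enters.** Table 1 of the combined protocol and SAP admits "Use of lorazepam, alprazolam, temazepam, clonazepam, and/or zolpidem for current or prior insomnia symptoms 2 or more nights per week". The dose ceiling is an exclusion: "Supratherapeutic/high baseline hypnotic dose (> diazepam-equivalent of 8 mg/night". Intermittent users are expected, because the Extended taper plan says: "Taper schedules for participants who used their hypnotic 'as needed' at baseline will be adjusted".

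**Randomization.** Stratification is meant to leave the groups "balanced in baseline hypnotic drug type half-life (i.e., temazepam/zolpidem; alprazolam/lorazepam; clonazepam) and gender". Neither factor measures nights of use or dose.

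**H1a model.** In the Primary Analysis Plan, discontinuation (yes/no) "will be regressed on treatment group assignment (MTcap vs. SGT+CBTI) in two logistic regression models", one post-treatment and one at 6 months. The covariates are fixed for every analysis: "We will include terms for stratification characteristics and covariates for baseline pain intensity, PHQ-9, and opioid use in all of the models". Multiple imputation is named for H1a, but its variables are not listed.

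**H1b model.** Frequency (0 to 7 days) and quantity (average daily diazepam-equivalent dose) are analysed in group-by-time mixed models in which baseline is one of the three time points.

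**Data.** Nights of use per week are asked at telephone screening. The Baseline Assessment section and Table 2 provide a hypnotic abstraction form, a prescription-database query and a one-week medication log.

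**The concern.** H1a is the first-listed hypothesis. It is the yes/no version of the behaviour that H1b measures as a count and a dose. For H1b the plan relies on baseline use to gain precision; for H1a it leaves baseline use out, without giving a reason, while adjusting for three less direct covariates.

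If people who use a hypnotic two or three nights a week stop at a different rate from nightly users, two things follow. The H1a test has less power than the data allow. And in a trial where the arms happen to differ on entry use, part of the observed difference reflects that. If the covariate is not prespecified and an imbalance then appears, adding it would be post hoc, and leaving it out would invite criticism.

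**Working it through.** **1. The plan's own figures.** Inputs from the Primary Analysis Plan are 57 per arm after 13% dropout from 132, with α and power given as "0.05, power=0.80, two-sided hypothesis tests, and intention-to-treat approach".

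- *H1b frequency.* SD 1.94 and r = 0.83 come from a prior study. The detectable effect on change scores is SD × √(2(1−r)) × (1.960 + 0.842) × √(2/57).
  - r = 0.83: 1.94 × 0.583 × 2.802 × 0.1873 = 0.594 (stated 0.60).
  - r = 0.77: 0.69 (stated 0.70).
  - No baseline: 1.94 × 2.802 × 0.1873 = 1.018 (stated 1.02).
  - By the plan's figures, using baseline cuts the detectable effect by 1 − 0.60/1.02 = 41%.
- *H1a.* The plan states a detectable difference of 21 to 26 points for control rates of 59% to 63%. The pooled two-sided formula gives 23.6 points (59%) and 22.7 (63%). No single formula tried returns the stated range, although the two-sided results lie inside it. That is a separate matter; about 23 points serves here as the yardstick.

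**2. Size of a chance imbalance.** The share p of low-frequency users and their gap g in discontinuation are not in the documents. I assume p = 25-50% and g = 20-30 points. The SD of the between-arm difference in share is √(2p(1−p)/57), and the shift in the unadjusted H1a difference is that SD × g.

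| p | SD of imbalance | Shift at 1 SD, g = 20 / 30 | Shift at 1.96 SD, g = 20 / 30 |
|---|---|---|---|
| 25% | 8.1 points | 1.6 / 2.4 | 3.2 / 4.8 |
| 40% | 9.2 points | 1.8 / 2.8 | 3.6 / 5.4 |
| 50% | 9.4 points | 1.9 / 2.8 | 3.7 / 5.5 |

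At p = 50%, an imbalance above 10 points has probability 29%. With all 66 per arm, the largest entry falls from 5.5 to 5.1.

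**3. How much of this the standard error already covers.** At 61% vs 84%, SE = √[(0.61×0.39 + 0.84×0.16)/57] = 8.1 points. The 1-SD shifts of 1.6 and 2.8 points are (1.6/8.1)² ≈ 4% and (2.8/8.1)² ≈ 12% of that variance. They are part of the reported uncertainty, not an addition to it.

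**4. Power with and without adjustment (simulation, 57 per arm).**

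- Binary low-frequency indicator, p = 40%, 3,000 trials per setting: 0.83 to 0.84 at g = 20; 0.82 to 0.85 at g = 30.
- Full planned covariate set plus nights and dose, 3,000 runs per setting, covariate mix assumed: change of 0, +1.3 and +3.3 points at g = 0, 20 and 30.
- Continuous baseline score with an assumed latent correlation with stopping, 61% vs 84%, 6,000 runs: 78% to 79% at 0.2; 80% to 83% at 0.4; 80% to 88% at 0.6.

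**5. Type I error.** In the continuous-score runs under the null (61% in both arms), overall error is 4.2% to 5.3% with or without adjustment. Among trials with imbalance beyond 1.5 SD, unadjusted error is about 6%, 9% and 11% at latent correlations 0.2, 0.4 and 0.6; adjusted error is about 4% to 6%.

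**6. Room in the model.** The planned terms use 7 degrees of freedom: treatment 1, drug group 2, gender 1, pain 1, PHQ-9 1, opioid use 1. Expected non-events at 61% vs 84% are 0.39×57 + 0.16×57 = 31.4, or 4.5 per degree of freedom. With 8 this falls to 3.9, and with 9 to 3.5.

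**The case against.** The case against acting has several parts.

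- **Randomization already covers chance imbalance.** This stands. A reader might infer that H1a is biased or its test invalid. The documents do not support that: allocation is random and overall type I error is near 5% either way. The raised error rates in step 5 apply only to trials selected for marked imbalance, under assumed correlations.
- **Nothing shows that baseline use is a strong predictor of stopping.** This also stands. A reader might carry r = 0.83 over to H1a. That figure comes from a prior study and describes days of medication use, not stopping after a supervised taper. Here every participant follows a taper to zero, and as-needed schedules are held to the person's own weekly baseline dose. It makes baseline use a reasonable candidate covariate and no more.
- **The arms treat as-needed users differently.** One could read the sentence "For the MTcap group, the capsules on the predetermined drug-free days will be filled with an inert filler substance" as evidence of confounding, since comparison participants take nothing on those days. It is a deliberate feature of the intervention and says nothing about a missing covariate.
- **The topic is partly handled elsewhere.** H1b will show baseline use by arm, drug group is in every model, and the dose range is capped. These help interpretation but do not adjust H1a.
- **A short covariate list is defensible with about 31 non-events.** This is fair, and it argues for adding one term rather than two, since average daily dose already depends on nights used.

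What remains is that the plan already accepts covariate adjustment, holds this variable, and gives no reason for leaving it out of H1a.

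**Conclusion.** The omission is confirmed in the text, and its consequence is modest. H1a loses some precision, and its estimate can shift when the arms differ on entry use. Under the assumed 25-50% share and 20-30 point gap, the shift at the 95% limit of imbalance is about 3 to 5.5 points against a detectable difference of about 23, and adjustment adds about 1 to 3 points of power. Share, gap and direction are all assumptions. If baseline use is only weakly related to stopping, the gain is about 1 point or less; the 8-point gain needs a latent correlation of 0.6, for which the documents give no evidence. The point is worth a sentence in the plan because the change is nearly free before unblinding and hard to defend afterwards.

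**What to change.** In the Primary Analysis Plan under H1a, prespecify baseline nights of hypnotic use per week as a covariate in both logistic models. List baseline nights per week and baseline average daily dose in diazepam equivalents among the variables of the H1a imputation model. Dose may also be added to the H1a models, but it overlaps with nights used. Stratification, eligibility and the taper rules stay as they are.

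The cost is one sentence and one degree of freedom (two if dose is added), with no new data collection. The constraint is the number of non-events. If post-treatment discontinuation is very high, there will be fewer than 31: were every MTcap participant to stop, as all did in the feasibility study, only 0.39×57 ≈ 22 would remain at a 61% comparison rate. That favours the single-term version.
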